Results are better in paroxysmal patients, than for persistent AF, also for CBA. [13] Nevertheless, persistent patients with normal left atrial dimensions made up an important proportion of our group. [15] Differentiation between paroxysmal and short term persistent becomes almost impossible from a clinical point of view, as patients get early cardioversion, before they are spontaneously reverted to sinus rhythm. [16] Real longstanding persistent patients, however were excluded from our and all previous trials, as were patients with very large atria. Larger atria have more recurrences than smaller atria. Successful ablation results in a smaller left atrial volume, which was shown in several studies with RF, also for paroxysmal patients. [17] This volume reduction is antiarrhythmic as well.

It has been hypothesized that early therapy prevents further progression of the disease. [16] This has never been proven for catheter ablation, while some pilot trials were promising. [18] Reduction of left atrial volume can be used as a substitute for antiarrhythmic efficacy and for less disease progression.

RATIONALE

Limited data indicate that ablation is better than AAD therapy. The 9 small randomized clinical trials as recently summarized by health care authorities with a correct methodology only included 971 patients, and only studied radiofrequency ablation. [19] However, there was substantial heterogeneity, with a majority of paroxysmal patients, but some had mixed groups. Endpoints in these trials were not always clear and variable as well. Side effects of ablation were somewhat neglected. Stop-AF only addressed paroxysmal patients (but included 22% cardioverted patients) and has recently been published. [14] This opens the perspective to organize a prospective trial comparing the efficacy and safety of CBA to standardized medication for treatment of paroxysmal AF and early onset persistent AF without structural heart disease. As elsewhere a trial is launched for first onset paroxysmal AF, we would like to focus in this protocol *on early onset persistent AF without structural heart disease*. The value of CBA in these patients has never been studied; the endpoints for persistent patients are much easier than for paroxysmal patients. Reduction in LA size can be compared versus patients on drug therapy and versus failing patients.

HYPOTHESIS

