1. The results of CBA in early onset persistent AF are better compared to standard medical therapy with as endpoint maintenance of sinus rhythm after 1 year and an improved QOL in the ablation group.
2. Successful CBA results in reduction of the LA volume.

INCLUSION/EXCLUSION CRITERIA

The total AF history is regarded for previous episodes, paroxysmal or persistent. ~~should be shorter than 24 months~~. Symptomatic patients can be included if they have had at

least 2 episodes in their total history, of which one within the last year. One episode in the entire history should have lasted more than 7 days **48 h**, requiring electrical or pharmacological cardioversion or stopped spontaneously after more than 7 days. The duration of this episode should be shorter than 1 year. If one episode is paroxysmal it should have been lasting minimal 30 sec.

All patients eligible for the study will sign informed consent, have an echocardiogram prior to inclusion to exclude severe left ventricular dysfunction, to rule out significant valve abnormalities, left ventricular hypertrophy and to assess the left atrial (LA) volume and diameter.

Prior to randomization, and after inclusion it is suggested to the local investigators to perform an MRI-scan or CT scan of the LA and pulmonary veins (in both branches of the study) in eligible patients to assess the anatomy and the left atrial volume. The results should not influence the strategy of treatment.

Inclusion criteria

- > 21 years and legally capable
- history of 2 symptomatic AF episodes more than 30 sec .
- At least one AF episode within the last year
- One episode cardioverted after more than 7 days or spontaneously terminated after more than 7 days; this episode should have been shorter than one year
- Eligible for at least one first step drug therapy (sotalol, propafenone, or flecainide) **and/or** for amiodarone

- Left ventricular ejection fraction estimated > 45%
- LA diameter < 50 mm (parasternal short axis) **and/or** LA volume less than 100 ml (apical view, Area Length method)
- No previous CVA or TIA (the latter with documented deficit on CT scan)
- ~~CHADS2VASC ≤ XXXX~~
- Failed AAD strategy, or untreated with AAD
- No use of Amiodarone in the previous 6 weeks (except IV or oral for 7 days)
- Informed consent

Exclusion criteria

- Age **> = 80** yrs
- CHF
- Ischemic heart disease as known in the history
- (Severe) Left ventricular hypertrophy as shown on echo (IVSd or PWd > 14 mm)

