 - after inclusion (month -1) and repeated at months 3 .This will be done with the study Holter without necessarily influencing the therapy (so called blanking period)
- 48 hour Holter: with a clinical device
 - at the end of 6 months .
- 7 days Holter: with a clinical device
 - at the end of 12 months .
- Clinical visits :

should be performed by the study nurses/supervised by the investigators

- At months 3, 6, and 12 months after ablation
- Additionally at month 0 for the drug arm, while the ablation group is admitted
- Office ECG ;
 - ° at month 3, 6 and 12
- Drug management:
 - AAD: After 3 months stop AAD in the ablation arm in those patients free of AF episodes.
 - OAC: After 6 months consider stopping oral anticoagulation, or replacing them with antithrombotic medication in patients free of AF episodes if the scores allow so.
- Echocardiogram:
 - At month 12 a new echocardiogram is obtained to assess the LA volume and diameter.
- QOL with disease specific questionnaire (AFQOL 18)
 - At baseline and at month 12
- Blood samples
 - At baseline and at months 6 and 12
 - Thyroid tests (TSH), liver function (AP, SGOT, SGPT), creatinine

- Drug diary
 - At baseline, at month 0 and at months 6 and 12 for all patients in both arms
- Cost calculation: data should be prospectively collected in CRF at the time of scheduled and unscheduled visits, based on costs as foreseen in the reimbursement of the RIZIV/INAMI and additional drug costs.

CROSS OVER

Is allowed after 6 months. This implies that at 12 months we will be able to do not only ITT but also OTA.

SERIOUS ADVERSE EVENTS

SAE's are expected to happen in 7% in the ablation arm, and at a rate of 12-15% in the drug arm, because of side effects and 3% because of proarrhythmia (20).

ENDPOINTS

Primary endpoints

- Sinus rhythm at clinical visit at 1 year after the ablation, or with AAD
- Freedom of AF with all measurements

Secondary endpoints

- Reduction of LA volume in successfully treated patients
- Number of cardioversions
- Percentage of patients on AAD after 6 and 12 months

- Vascular complications
- Stroke, TIA
- SAE in both groups
- Number of cross-overs (with OTA)

[figure not shown]

Figure 1. AAD : antiarrhythmic drugs; LA: left atrial; QOL: quality of life; R: randomization

STUDY ORGANISATION

Steering committee : [name], [name], [name], [name]

DMSB : [name], [name], [name]

One central study coordinator (University Hospital Ghent) – [name]

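### The only listed left atrial (LA) volume endpoint, and Hypothesis 2, cover only patients selected by success, so the supplied protocol text attaches no randomised comparison to LA volume

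*Protocol*

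**What the plan says.** The protocol deals with LA volume in five places.

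- **Background** gives it a causal role: "Reduction of left atrial volume can be used as a substitute for antiarrhythmic efficacy and for less disease progression". It also links LA size and rhythm outcome in both directions: "Larger atria have more recurrences than smaller atria", and, of the shrinkage after ablation, "This volume reduction is antiarrhythmic as well".
- **Rationale** mentions comparators: "Reduction in LA size can be compared versus patients on drug therapy and versus failing patients".
- **Hypothesis 2** names none: "Successful CBA results in reduction of the LA volume".
- **Endpoints, Secondary endpoints** has a single LA item: "Reduction of LA volume in successfully treated patients". It does not say whether one arm or both are meant.
- **Measurement** is not limited by arm or by success. The echocardiogram before inclusion serves, among other things, to examine "left ventricular hypertrophy and to assess the left atrial (LA) volume and diameter", and under Follow up "At month 12 a new echocardiogram is obtained to assess the LA volume and diameter".

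The Cross over section says that both ITT and OTA (read here as an on-treatment analysis) will be possible at 12 months. It names no endpoint.

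**The concern.** Whether a patient is successfully treated is settled only during follow-up. Patients kept on that basis are no longer the groups that randomisation made comparable. The Background itself gives reasons to expect successes to differ in LA size, or in LA change, for causes other than the assigned treatment.

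At stake is what the LA result may be used for. If the listed wording is followed, the trial reports LA change in a selected group. That cannot support a statement that assignment to CBA reduced LA volume, and so it cannot bear the weight that the Background puts on LA reduction as a stand-in for efficacy and slower progression.

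The selecting condition is also undefined. There are two primary endpoints: rhythm at the one-year visit, and absence of AF across all measurements. A patient with AF on an earlier Holter who is in sinus rhythm at the one-year visit succeeds on the first and fails on the second. Unless the choice is stated beforehand, the LA population could be fixed after the results are seen.

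**Working it through.** **Inputs (protocol, Sample size):** success 50% on drugs and 72% with CBA; power 0.80; significance 0.05; 76 per arm; 167 in total with 10% loss. The supplied text gives no expected LA change, no SD and no sample size for LA volume.

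**The plan's own figure.** Two-sided test, pooled variance, no continuity correction:

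n = [1.960 × √(2 × 0.61 × 0.39) + 0.842 × √(0.50 × 0.50 + 0.72 × 0.28)]² / 0.22² = 76 per arm, as stated.

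The total of 167 is 152 × 1.10 = 167.2. Dividing instead, 152/0.90, gives 169. The difference is two patients and does not affect this point.

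**Who is kept**, with 76 evaluable per arm:

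- CBA successes: 0.72 × 76 = 54.7, about 55. Drug successes: 0.50 × 76 = 38.
- Secondary endpoint, if both arms are meant: 55 + 38 = 93 kept; 59 of 152 (39%) left out.
- Hypothesis 2, CBA successes only: 55 kept; 97 of 152 (64%) left out.

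**How far selection alone could move a comparison.** Suppose treatment has no effect on LA volume. Let each patient have a standard normal prognosis score, with success when the score exceeds a threshold set by the arm's success rate. Let LA reduction (in units of its own SD) have correlation r with that score. The mean score among the top 72% is φ(z)/0.72 = 0.468, where z cuts off the lower 28%. Among all drug patients it is 0.

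CBA successes against all drug patients (55 vs 76) is one reading of the Rationale. Its bias is r × 0.468:

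| assumed r | bias (SD), positive = favours CBA |
|---|---|
| −0.5 | −0.23 |
| −0.2 | −0.09 |
| 0 | 0 |
| 0.2 | 0.09 |
| 0.5 | 0.23 |

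The Rationale's other comparator is failing patients. Within CBA the failures have a mean score of −1.202, so the bias is r × (0.468 + 1.202) = 1.670r: 0.33 to 0.83 SD towards Hypothesis 2 at r = 0.2 to 0.5, and the reverse at negative r.

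The documents give no r. It could be positive if patients with a good prognosis shrink more. It could be negative if successes start with smaller atria and have less room to shrink.

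**What an ITT comparison could detect** (80% power, two-sided 5%, before any gain from baseline adjustment): 2.802 × √(2/76) = 0.4545 SD. If a share c of drug patients crosses over and gains the full effect (assumed), this becomes 0.4545/(1 − c): 0.505, 0.568 and 0.649 SD at c = 0.1, 0.2 and 0.3.

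If shrinkage of d SD follows success equally in both arms, the ITT difference is only (0.72 − 0.50)d = 0.22d. With variance 1 + p(1 − p)d² in an arm with success rate p, power is about 10% at d = 0.5 and 23% at d = 1. If only CBA successes shrink, the difference is 0.72d and 80% power needs d of about 0.64.

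**The case against.** The strongest reply is that Hypothesis 2 is deliberately about successes and the listed wording answers it. No hypothesis states that assignment to CBA changes LA volume; the substitute role is a Background premise, not an objective. An ITT comparison therefore adds a question, and where shrinkage simply follows success it has little power. This largely stands. It is why the success-based analysis should stay, and why a null ITT result would not refute shrinkage in successes. It does not remove the mismatch between a Rationale that invokes drug-treated patients and an endpoint list that leaves them out as a comparator.

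A second reply is that ITT is already foreseen at 12 months, when the LA echocardiogram is done. That sentence is general, and the LA item names a different population. At best the two need reconciling.

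A third is that the SAP may settle the analysis set, the adjustment and the missing-data rule. It may. The SAP text was not available and Figure 1 is not shown, so nothing here says that the SAP lacks such an analysis.

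A reader might also infer that the plan builds in a bias favouring CBA. The documents do not support that: r is assumed, its sign is unknown, and the protocol fixes no between-group LA comparison to which a bias could attach. In particular, no section proposes comparing CBA successes with drug successes.

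**Conclusion.** The point holds as a gap in specification, not as a demonstrated distortion. In the supplied protocol text, the LA endpoint and Hypothesis 2 both condition on an outcome that arises after randomisation, and neither the Rationale's comparison with drug-treated patients nor the ITT statement is attached to LA volume. The result as listed is descriptive of successes.

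The shares left out (39% and 64%) rest on the planned success rates and 76 evaluable patients per arm. The bias range rests on an assumed normal selection model and an assumed r, and includes zero.

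It would be too strong to say that Hypothesis 2 cannot be answered or that the trial's main result is compromised: the listed wording does address Hypothesis 2, and the primary endpoints and sample size are unaffected. Severity is low to moderate.

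**What to change.** 1. Reconcile the Rationale, Hypothesis 2 and the secondary endpoint list, and confirm the result against the SAP.
2. Unless the SAP already has it, add a secondary analysis: month-12 echocardiographic LA volume compared between randomised arms by ITT, adjusted for baseline LA volume, with a stated rule for missing month-12 echocardiograms.
3. Keep the success-based analysis for Hypothesis 2, label it non-randomised, and say whether it covers one arm or both.
4. State which primary endpoint defines successful treatment.

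The cost is wording and one extra analysis; no visits, measurements or patients are added. The drawback is limited power, made worse by cross-over after month 6. The plan should say in advance that a null ITT result does not rule out shrinkage in successes.
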